## 7. SAFETY

### 7.1 Potential risks & benefits to study participants

There are no major anticipated personal safety risks associated with patients taking part in this study, though it is recognised that the – particularly incorrect – application of compression and cooling devices can result in skin reactions and discomfort and can potentially affect blood flow. If the research team learns of important new information that might affect the patient's desire to remain in the study, he or she will be told. Appropriate precautions are in place to ensure medical and personal information is kept safe through adhering to appropriate governance regulations. Any adverse events will be recorded, as outlined in sections below.

For the participants in the control group there is no direct benefit in taking part in this study. They will be cared for in exactly the same manner as they normally would. For participants in the VPULSE

intervention group, there may be benefits in terms of improved pain control compared to normal standard care. Although there is initial evidence that this is indeed the case, this has not yet been proven and established through a prospective randomised trial, and this study is aimed to assess this. Participants cannot claim payments, reimbursement of expenses or any other benefits or incentives for taking part in this research.

## 7.2 Safety reporting window and definitions

Adverse Event (AE)	
Any untoward medical occurrence in a patient or other clinical investigation participant taking part in a trial of a medical device, which does not necessarily have to have a causal relationship with the device under investigation.
 
An AE can therefore be any unfavourable and unintended sign (including an abnormal laboratory finding), symptom or disease temporally associated with the use of the device, whether or not considered related to the device.

Serious Adverse Event	
A serious adverse event is any untoward medical occurrence that:
 
 
- results in death
 
- is life-threatening
 
- requires inpatient hospitalisation or prolongation of existing hospitalisation
 
- results in persistent or significant disability/incapacity
 
- consists of a congenital anomaly or birth defect.
 
 
Other 'important medical events' may also be considered serious if they jeopardise the participant or require an intervention to prevent one of the above consequences.
 
NOTE: The term "life-threatening" in the definition of "serious" refers to an event in which the participant was at risk of death at the time of the event; it does not refer to an event which hypothetically might have caused death if it were more severe.

The safety reporting window for (Serious) Adverse Events is from start of the index surgery to up to and including 30 days after the index surgery. Any unscheduled medical or surgical care received by the participant outside this window is not included for safety reporting for this study. This aligns with national 30-day reporting standards for eg infection and mortality after surgery.

## 7.3 Procedures for recording adverse events

All SAEs need to be reported to the sponsor/host Trust R&D **within one working day** of the investigator team becoming aware of them – AEs should be reported on within two weeks of

becoming aware of them. For this purpose an AE report form is completed by the researcher and/or Chief Investigator

The relationship of each adverse event to the trial must be determined by the Chief Investigator, or – only in cases where the CI is not available - another suitably qualified and delegated clinically qualified person (doctor or orthopaedics specialist nurse), according to the following definitions:

- **Related:** The adverse event follows a reasonable temporal sequence from swabbing. It cannot reasonably be attributed to any other cause.
- **Not Related:** The adverse event is probably produced by the participant's clinical state or by other modes of therapy administered to the participant.
- **Severity grading:** the Chief Investigator or – only in cases where CI is not available - suitably clinically qualified delegated person (doctor or orthopaedics specialist nurse) will also record if it concerns an AE or SAE.

This is recorded on the aforementioned AE reporting form. The forms are stored in the study site file.

Pseudo-anonymised copies of all adverse events forms will be shared with Joint Operations Ltd as soon as causality reporting has been performed and concluded.

If the CI did not perform causality of the (S)AE for a particular case, he/she will check the completed forms and countersign the case as soon as he/she is available to do so.

## 8. STATISTICAL CONSIDERATION AND DATA ANALYSIS PLAN

### 8.1 Analysis of baseline characteristics

To determine the demographics and characteristics of the patients in the two arms the following data will be collated:

- Age (yrs)
- Gender
- Height (kg), weight (cm), BMI

Data concerning the actual knee replacement procedure will also be collected, including:

- Type of surgery
  - Including type of medical device used and which leg operated on
- Length of operation (min) and blood loss (ml) during operation
- Type of anaesthetic and analgesics prescribed post-surgery
- Hospital length of stay (days)
- Moment physiotherapy and early recovery initiated
- Type of standard bandaging applied if control patient.

Any differences in distribution will be established with Chi-squared test or Mann-Whitney U-test/t-test (depending on distribution of data) as indicated.

## 8.2 Primary outcome statistics

To determine the level of operation-site related pain experienced at day 2 post-operation and to compare the average pain scores of patients in the control and intervention arm respectively, through administration of 10 cm visual descriptor scale (VDS) for pain.

The study is powered to detect the established minimal clinically important difference (MCID) of 1.5 cm on a 10 cm VDS pain.

The average difference between time points will be calculated per group, 2 days post-surgery being the primary endpoint. 24hrs, 3, 5, 12 days and 6 weeks post-surgery will also be analysed. To compare the groups, the Mann-Whitney U-test will be applied.

To avoid relying on one outcome measure related to pain, at 3, 5, 12 days, and 6 weeks post-surgery pain perception will also be measured using the short form McGill pain questionnaire. Again, to compare groups the Mann-Whitney U-test will be applied.

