## RESEARCH PROTOCOL SUMMARY

TITLE:	A single-centre, two-arm, controlled, prospective randomized trial comparing AIRCAST® KNEE CRYO/CUFF™ passive compressive cryotherapy with VPULSE® active compressive cryotherapy after knee arthroplasty surgery
Short title:	ALASKA trial: Assessment of cooling Application poSt Knee Arthroplasty
IRAS number	322564
Device description	
VPULSE®
 
VPULSE® is designed to improve patient outcomes after injury and / or surgery through reduction of pain and swelling, with the aim to reduce the need for medication.
 
The VPULSE® system is used with anatomically designed pads, providing a continuous flow of cold and intermittent dynamic compression therapy.
 
Motorised cold therapy intended to reduce operative site discomfort and inflammation.

Study type	Medical device trial, involving CE-marked devices used for intended purpose.
Study design	Single-centre, two-arm, controlled, prospective randomized trial.
Patient population	
Adult participants who have unilateral knee replacement surgery (knee arthroplasty) and who meet the study inclusion criteria Participants must have the capacity to provide informed written consent and complete patient reported outcome measures.
 
The study has the following sample parameters: standard deviation of 2 cm per cohort, power beta of 80%, alpha p-value of 0.05. Sample size takes into account 30% attrition rate, effect size of 0.75 (mean difference of 1.5cm on 10cm visual analogue scale) based on previous ROBOT trial results.
 
Total of 88 patients:
 
 
- 44 Patients to receive AIRCAST® KNEE CRYO/CUFF™ (current standard care, control arm)
 
- 44 Patient to receive VPULSE® with knee-specific cuff (intervention arm)
 

Primary objective	To determine the level of operation-site related pain experienced at day 2 post-operation and to compare the average pain scores of patients in the AIRCAST® KNEE CRYO/CUFF™ and VPULSE® arm respectively, through administration of 10 cm visual descriptor scale (VDS) for 'at rest' pain.

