### **5.5 Outcome measures**

#### **5.5.1 Primary outcome measures**

To determine the level of operation-site related pain experienced at day 2 post-operation and to compare the average pain scores of patients in the control and intervention arm respectively, through administration of 10 cm visual descriptor scale (VDS) for pain.

The study is powered to detect the established minimal clinically important difference (MCID) of 1.5 cm on a 10 cm VDS pain.

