## 6. SUBJECTS

### 6.1 Anticipated number of research subjects

The sample size calculation does take into account a 30% patient attrition rate (withdrawal and loss to follow-up), since this involves a study with multiple time points for data collection up to 12 weeks. From other similar studies we are aware that loss to follow-up is relatively high in this group of patients. Patients will be recruited from the adult (age 18+) population routinely seen by the evaluating clinical staff members. The primary outcome measure is based on knee/leg (ie wound site) pain experienced 5-days post-surgery based on the VDS pain scale 'at rest'. The hypothetical difference in pain perception is 1.5 on a 10 cm scale which equates to a significant 'minimally clinically important difference' for pain (Kelly 2001; Lee et al 2003; Tashjian et al 2009). The values and differences observed in the ROBOT trial will be used for reference.

The non-parametric two-sided Mann-Whitney u-test is applied because the data is ordinal; 80% power and 5% significance is also applied. A priori power calculations using GPower 3.1 software, result in the following sample size summarized in Table 3.

Analysis will be performed on an intention-to-treat basis, although the number of days that a participant has worn a bandage will be recorded.

Table 4, Sample size calculation

	Mean pain score at 5 days post-op	Standard Deviation
Arm A (hypothetical)	5.0	2
Arm B (hypothetical)	3.5	2
	Power beta of 80%, Alpha p-value of 0.05, Effect size 0.75  Sample size required without any drop-out: 62 Sample size with 30% attrition rate included: 88  Total of 88 patients: 
 
- 44 Patients to receive AIRCAST® KNEE CRYO/CUFF™ device (current standard care, control arm)
 
- 44 Patient to receive VPULSE® (intervention arm)
 
	

The CONSORT guidelines require a statement on the number of patients assessed for eligibility (Schulz, Altman & Moher 2010). The number of patients screened but who did not meet the inclusion criteria or who declined to participate will be recorded, as will any patients who are lost to follow-up (Appendix 3).

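### Section 8.2 does not fix the primary variable (pain score or difference between time points); the planned power belongs to the score, and the collected baseline is unused

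*Protocol*

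**What the plan says.** Protocol section 5.5.1 gives the aim as to "compare the average pain scores of patients in the control and intervention arm respectively", and section 8.2 opens by repeating it. Section 8.2 then adds: "The average difference between time points will be calculated per group, 2 days post-surgery being the primary endpoint". It does not say which time points are differenced or whether baseline is one of them. The next instruction on testing is "To compare the groups, the Mann-Whitney U-test will be applied", with no covariate. The section also gives 1.5 cm as the difference the study is powered to detect.

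Section 6.1 sizes the trial on the score itself. Table 4 sets hypothetical values of 5.0 and 3.5 under the column "Mean pain score at 5 days post-op", each with SD 2. The test is fixed there too: "The non-parametric two-sided Mann-Whitney u-test is applied because the data is ordinal".

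The at-rest VDS is measured before surgery (protocol summary and Table 3). The only model with covariates is the Cox regression in section 8.3. It is listed under secondary outcomes, and the covariates it refers back to do not include baseline VDS.

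**The concern.** The primary comparison should leave an analyst no choice about what goes into the test. Read literally, section 8.2 allows two variables: the post-operative score, or a difference between that score and an unnamed other time point. If the choice is still open when data are available, it can be made after seeing results.

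The two variables also differ in power. The sample size uses the SD of a score. The SD of a change depends on how strongly the two measurements correlate, and the protocol gives neither that correlation nor an SD of change. The baseline may be taken up to 12 weeks before surgery and reflects pre-operative knee pain rather than acute surgical pain, so a weak correlation is possible, though nothing in the protocol establishes it.

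Two lesser matters follow. A baseline measurement that could sharpen the comparison at no extra burden is left out of it. And the target is stated in centimetres, while the only inferential output named for the primary comparison is a rank test.

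**Working it through.** **Inputs from the protocol**
- Difference: "The hypothetical difference in pain perception is 1.5 on a 10 cm scale" (section 6.1); Table 4 gives 5.0 against 3.5.
- SD: "standard deviation of 2 cm per cohort" (summary), also in Table 4. Effect size 1.5/2 = 0.75.
- Error rates: "80% power and 5% significance is also applied" (section 6.1), two-sided Mann-Whitney.
- 62 without drop-out, i.e. 31 per arm; 88 after 30% attrition.

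**Assumed, because the protocol is silent**
- Correlation ρ between baseline and post-operative at-rest VDS: 0 to 0.7.
- SD 2 at baseline as well, normally distributed scores, and a 1.5 cm difference on either variable.

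**Step 1. Reproduce the plan's figure.** Approximate Mann-Whitney power by a noncentral t with the sample size multiplied by 3/π, its relative efficiency for normal data:
- effective n per arm = 31 × 3/π = 29.6
- noncentrality = 0.75 × √(29.6/2) = 2.885
- degrees of freedom = 2 × 29.6 − 2 = 57.2
- power = 81.0%

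The smallest n per arm that reaches 80% is 31, so the total of 62 reproduces exactly. Simulation (6,000 trials per setting) gives 80% to 81%. For attrition, 62/0.7 = 88.6, against 88 stated; this is rounding and of no consequence. The planned power therefore belongs to a Mann-Whitney test on the raw score.

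**Step 2. Test change from baseline instead.** SD of change = √(2² + 2² − 2ρ·2·2) = 2√(2(1−ρ)). This equals 2 at ρ = 0.5, is larger below that and smaller above it.

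**Step 3. Test the score adjusted for baseline (ANCOVA).** Residual SD = 2√(1−ρ²), with t-based power and no 3/π factor. No degree of freedom is deducted for the covariate, which flatters ANCOVA slightly.

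Power at 31 per arm:

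| ρ (assumed) | SD of change | Mann-Whitney on change | Mann-Whitney on score | ANCOVA on score | Total needed for 80% on change |
|---|---|---|---|---|---|
| 0 | 2.83 | 52% | 81% | 83% | 120 |
| 0.2 | 2.53 | 61% | 81% | 84% | 96 |
| 0.3 | 2.37 | 67% | 81% | 86% | 84 |
| 0.4 | 2.19 | 74% | 81% | 89% | 74 |
| 0.5 | 2.00 | 81% | 81% | 92% | 62 |
| 0.6 | 1.79 | 89% | 81% | 95% | 50 |
| 0.7 | 1.55 | 96% | 81% | 98% | 38 |

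Totals are before attrition. Simulated power for the change score at ρ = 0, 0.2, 0.3, 0.5 and 0.7 was 51%, 61%, 67%, 81% and 96%, in agreement.

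**Step 4. Separate adjustment from the normality assumption.** At ρ = 0 the covariate explains nothing, yet ANCOVA shows 82.8% against 81.0%. That gap of 1.8 points comes only from dropping the 3/π factor. The gain from adjustment itself is the ANCOVA figure minus 82.8%: 84.3 − 82.8 = 1.5 points at ρ = 0.2, 86.1 − 82.8 = 3.3 at 0.3, and 91.8 − 82.8 = 9.0 at 0.5.

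**The case against.** A reader might infer that the plan has settled on a change-from-baseline analysis and is therefore underpowered. The document does not support this. Section 8.2 never names baseline. Its opening aim, section 5.5.1, the summary and Table 4 all speak of scores, and the sentence on differences can be read as a description within each arm, separate from the test between arms. Even on the change reading, power falls below 80% only for a correlation below about 0.5; above that, the change score gains power.

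Nor is the Mann-Whitney test an error. Section 6.1 names it, gives a reason and sizes the trial for it, so it costs nothing against the plan.

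It is also tempting to say that the trial will give no estimate in centimetres. A p-value from the rank test indeed cannot be compared with 1.5 cm. But a Hodges-Lehmann shift in cm with an interval can accompany that test, and such estimates are commonly left to a statistical analysis plan, which is not at hand. Their absence from the protocol is not a defect in itself.

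Finally, the advantage of ANCOVA at low correlation is small and partly due to assuming normality. On bounded or skewed pain scores the rank test need not be the weaker one.

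These objections remove any claim of an established power loss. What stands is that one sentence in the primary analysis is undefined, that one reading of it breaks the link to the sample size, and that a collected baseline is unused.

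**Conclusion.** The point holds as an ambiguity with a cheap improvement attached. Section 8.2 does not fix one primary variable. The stated 80% power holds for the raw score (81% reproduced). It does not carry over to change from baseline, where power would run from 52% at correlation 0 to 96% at 0.7 and crosses 80% near 0.5. These figures assume normal scores, SD 2 at both times and 31 completers per arm, with the correlation assumed throughout.

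Under the same assumptions, baseline-adjusted ANCOVA on the score has about 83% to 98% power for correlations of 0 to 0.7, of which about two points over Mann-Whitney come from normality rather than adjustment. It also yields directly a difference in cm to set against 1.5 cm. The change is worth making, but the plan as written is not shown to be underpowered.

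**What to change.** First settle the primary time point. Section 8.2 says day 2, section 6.1 says day 5, and Table 3 has no day-2 VDS column. That is a separate issue, but the wording below cannot be completed until those passages are reconciled.

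Then, in section 8.2:
- State that the primary variable is the at-rest VDS score itself at the primary time point, not a change, and delete or define the sentence on differences between time points.
- Analyse it by ANCOVA with arm and baseline at-rest VDS; surgery type (partial or total) may be added.
- Report the adjusted mean difference in cm with its 95% confidence interval, read against 1.5 cm.
- Keep the Mann-Whitney test on the score as the supportive analysis.

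Once the time point is settled, this costs analysis wording only: the baseline is already collected, and 62 completers remain sufficient under the plan's assumptions. The downside is a linear model on a bounded scale, which the supportive rank test covers.

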The above evidence regarding compression therapy involves bandaging of the most of the leg (from above knee to below ankle). VPULSE® has developed a device that combines active compression of the knee and cryotherapy. This concept is not necessarily novel; Song and colleagues summarised data from 10 randomised controlled trials, involving 522 patients in a meta-analysis of compressive cryotherapy versus cryotherapy alone in knee arthroplasty patients (Song et al, 2016). The conclusion from said study was that pain levels at up to a week post-operation were lower in the combined cryotherapy group compared to the cryotherapy only group. A 10-cm visual analogue scale for generic pain intensity was commonly deployed; the type of pain was not described in any of the studies. Similarly, cryotherapy reduces pain levels in the majority of studies conducted to date but again this is for generic pain intensity (Thacoor and Sandiford, 2019). A limitation with all treatment modalities (compression, cryotherapy or a combination of the two) is that there is a lot of variation in terms of the devices used and their application (frequency or duration).

In summary, there is a body of evidence that both compression alone, cryotherapy alone, and combined compression cryotherapy can all contribute to lower pain levels in patients after knee arthroplasty. As in the osteotomy study (ROBOT), we will here assess the levels of pain after knee replacement and also the pain profile (what type of pain experienced at what time point) when

patient are either using passive compression cryotherapy AIRCAST® KNEE CRYO/CUFF™ or active compression cryotherapy VPULSE®. The need for contemporary appraisals can be illustrated with one example publication from 2006 in which cryotherapy was compared to epidural for pain control (Kullenberg et al, 2006); the average length of stay in hospital was over 5 days in that study. Nowadays length of stay rarely exceeds 2 days, demonstrating the overall improvements made in managing post-surgery recovery of patients.

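### Pain is compared visit by visit with separate Mann-Whitney tests, so nothing planned tests whether the device effect changes over time; one baseline-adjusted repeated-measures model would do so cheaply

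*Protocol*

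**What the plan says.** Protocol section 8.2 names day 2 as the primary endpoint and continues: "24hrs, 3, 5, 12 days and 6 weeks post-surgery will also be analysed. To compare the groups, the Mann-Whitney U-test will be applied". The McGill scores at the later visits are handled in the same way. Section 8.2 also mentions an average difference between time points, but this is computed within each arm. Even if it were read as change scores that are then compared between arms, the comparison would still be made one visit at a time.

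The only regression named for pain is the Cox model in section 8.3. It does not model a repeated score, and the covariates listed for it do not include baseline pain. Table 3 nevertheless schedules VDS and McGill before surgery and at 24 hours, days 3, 5 and 12, and 6 weeks.

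On purpose, section 2 reports that the earlier osteotomy trial found a change in the type of pain and in its course over time. It says this trial will likewise assess pain levels and "the pain profile (what type of pain experienced at what time point".

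Section 6.1 plans for "a 30% patient attrition rate (withdrawal and loss to follow-up", states "Analysis will be performed on an intention-to-treat basis", and justifies the test thus: "The non-parametric two-sided Mann-Whitney u-test is applied because the data is ordinal; 80% power and 5% significance is also applied".

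**The concern.** A test at each visit answers whether the arms differ at that visit. It does not answer whether the difference at day 3 is larger than the difference at day 12. With about 80% power per test, some visits will miss significance by chance even when the effect is the same throughout. A reader who compares significant with non-significant visits may then see a benefit that starts, stops or returns when nothing has changed.

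Separate tests also leave information unused. They ignore the correlation between a patient's scores and the baseline score already collected. If patients without a score at a visit simply drop out of that visit's test, the visits compare different subsets of those randomised.

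**Working it through.** **Inputs from the protocol.** Difference: "The hypothetical difference in pain perception is 1.5 on a 10 cm scale" (section 6.1). Spread: "standard deviation of 2 cm per cohort, power beta of 80%, alpha p-value of 0.05" (summary). Table 4: "Power beta of 80%, Alpha p-value of 0.05, Effect size 0.75", with 62 evaluable patients and 88 after attrition. Five post-operative pain visits are scheduled in Table 3; there would be six if day 2 is added.

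**Reproducing the plan's sample size.** Effect size = 1.5/2 = 0.75. With the noncentral t distribution and the Mann-Whitney efficiency 3/π, power is 0.796 at 30 per arm and 0.810 at 31 per arm. Hence 31 per arm, or 62, as stated. Attrition: 62/0.7 = 88.6, against the stated 88. At 44 per arm the power is about 0.92.

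**Closed-form check with uncorrelated visits.** If each of five tests has power p, the chance of a mixed picture is 1 − p⁵ − (1 − p)⁵.
- 31 per arm: 1 − 0.81⁵ − 0.19⁵ = 1 − 0.349 − 0.000 = 0.65.
- 44 per arm: 1 − 0.924⁵ − 0.076⁵ = 1 − 0.674 − 0.000 = 0.33.

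**Simulation with correlated visits.** Normal scores, SD 2 cm, the same true effect at all five visits, a two-sided 5% Mann-Whitney test at each visit, and 4000 trials per setting. The correlation is not in the protocol, so it is varied. Effects of 1.0 and 2.0 cm are also assumptions. Entries are the share of trials with some visits significant and some not.

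| Constant effect | Per arm | r = 0 | r = 0.3 | r = 0.5 | r = 0.7 | r = 0.9 |
|---|---|---|---|---|---|---|
| 1.5 cm | 31 | 66% | 54% | 46% | 37% | 21% |
| 1.5 cm | 44 | 33% | 27% | 24% | 19% | 12% |
| 1.0 cm | 31 | – | 80% | 69% | 55% | – |
| 1.0 cm | 44 | – | 77% | 65% | 52% | – |
| 2.0 cm | 31 | – | 14% | 13% | 10% | – |
| 2.0 cm | 44 | – | 2% | 2% | 2% | – |

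A separate run of 1500 trials per setting gave 57%, 45% and 36% at 1.5 cm, 31 per arm and r = 0.3, 0.5 and 0.7. This is the source of the upper end of the quoted 37–57% range. With six visits the 31-per-arm shares at 1.5 cm rise to 72% at r = 0 and 24% at r = 0.9; with 44 per arm they run from 37% to 12%. If correlation decays with the number of visits between measurements (0.7 between neighbours), 31 per arm and six visits give 52%.

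A stricter reading is that significance switches at least twice, so that the effect appears to come and go. At 1.5 cm, 31 per arm and five visits this occurs in 44%, 37%, 32%, 25% and 14% of trials at r = 0, 0.3, 0.5, 0.7 and 0.9.

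**What a joint analysis gives on the same data.** A group-by-time test wrongly signals a changing effect in about 4–5% of trials at 31 per arm. The effect averaged over five visits has variance SD²(1 + 4r)/5 per patient. At r = 0.5 this is 4 × 3/5 = 2.4, and simulated power is 0.96. At r = 0.3 and 0.7 it is 0.99 and 0.92.

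**Attrition.** Suppose about 32% are lost by the last visit and the log-odds of dropout rise with previous pain. The observed-case difference at the last visit then falls from 1.50 to 1.44 cm at 0.5 per SD (0.06 cm) and to 1.29 cm at 1.0 per SD (0.21 cm). Both dropout strengths are assumptions.

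**The case against.** Several points on the other side stand.

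- A Mann-Whitney test at a visit is valid for the question whether the arms differ then, and section 6.1 gives a reason for choosing it.
- The formal objectives in sections 4.1 and 4.2 name pain reduction and type of pain, not a changing device effect. The profile in section 2 is largely type of pain by time.
- No text says that time-course conclusions will rest on which visits are significant.
- Using 31 per arm at every visit is pessimistic. Section 6.1 links the 30% loss to follow-up of 12 weeks, whereas pain scores end at 6 weeks, so early visits should be nearer 44 per arm.
- A constant effect to 6 weeks is only one scenario. Section 3.1.1 ends control device use by 48 hours or discharge, and section 3.1.2 calls the arms otherwise identical, so a fading effect would be real.
- Handling of missing scores may be set out in an analysis plan that is not shown.

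These points limit the size of the problem but do not remove it. Section 8.2 itself fixes the visit-by-visit method, and section 2 does bring in the course over time. If the effect fades, separate tests still do not test the fading; an arm-by-visit term does.

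A reader might infer that the trial will usually report a false time pattern. At the design effect this fails: with five equally correlated visits it is the majority outcome at 31 per arm only up to a correlation of about 0.4, and at 44 per arm for none of the correlations tried.

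**Conclusion.** The point holds as an advisable improvement to the secondary analysis. The protocol states an interest in the course of pain, collects baseline and repeated scores, and then fixes a method that neither tests a change in the device effect nor is stated to use baseline.

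The risk depends on readers interpreting the pattern of p-values. Under that condition, and with a constant 1.5 cm effect over five visits, about 37–57% of trials would show a mixed picture at 31 per arm and at most about 33% at 44 per arm. It becomes the majority only with weakly correlated visits or a true effect nearer 1.0 cm. The figures assume normal scores, equal SD at every visit, complete data at the stated size, and the correlations shown.

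Two stronger readings are not supported. The primary comparison is a single test and is not weakened by this point. Large attrition bias cannot be claimed either: the 0.06 to 0.21 cm at the last visit depends wholly on assumed dropout strength, and the protocol does not say how missing scores will be treated.

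**What to change.** Keep one primary time point and its test. For the secondary VDS and McGill scores over time, make the main analysis one repeated-measures mixed model per score with arm, visit, arm-by-visit and baseline score. Report the arm difference with its 95% confidence interval at each visit, and base any statement on the time course on the arm-by-visit term. Keep the Mann-Whitney tests as a sensitivity analysis. The model uses all available post-operative scores, which also reduces dependence on who answered at a given visit, provided that dropout is explained by observed scores.

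Two conflicts must be reconciled before this is written in:

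- **Primary time point.** It is day 2 in the summary and sections 5.5.1 and 8.2, but day 5 in section 6.1. Table 3 has no day 2 column. The answer decides which visits are secondary and whether there are five or six.
- **Withdrawn patients.** Section 5.3 keeps data collected up to withdrawal; section 6.3 excludes them. The model's population cannot be defined until one rule applies, and the intention-to-treat statement in section 6.1 bears on that choice.

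The cost is a change of wording and one model per score, with no new data or patients. The small downside is a parametric model on a bounded score, which the retained rank tests help to check.
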